6.4 Study Intervention Adherence

Intervention sessions will be scheduled approximately 1 week apart. At the end of each visit, the interventionist will schedule the next session to enhance adherence. If a participant misses a scheduled intervention appointment, study staff will attempt to reschedule the appointment for later in the week. If needed, two intervention visits may occur in the same week, with at least 2 days in between (e.g., Monday and Thursday or Tuesday and Friday).

To ensure adherence to the protocol, we will use tracking procedures that have proven effective in prior studies. Meticulous tracking procedures increase the likelihood that attrition will be random rather than systematic. Participants are enrolled in the study for approximately 12 months. During this time, in addition to their Enrollment Visit and at Month 4, Month 8, and Month 12 follow-up study visits, staff will contact participants monthly to review their most current contact information, address any concerns they have with the study, address scheduling issues or barriers to keeping study visit appointments (e.g., review train/bus routes and times, check for accuracy of plans), and stay connected with the participant (i.e., follow-up calls). Additionally, staff will contact participants to remind them of their appointments the week before their scheduled study visit and again the day before the scheduled visit (i.e., reminder call). All contacts and contact attempts will be recorded in the local contact tracking log.

When filling out the Contact Information Worksheet, staff will follow the instructions and ask for permission to send mail to a residential address, to leave a voicemail on contact phone lines, to send text messages, or to provide the name of the study to any person who is not the participant who may respond to telephone calls. Staff will ask how they should identify themselves when reaching out (e.g., *Calling from xxx regarding a research study*). In completing the Contact Information Worksheet, staff will obtain as much contact information as possible, including the participants' email addresses and phone numbers, social media contact information, and the contact information of at least two people (i.e., secondary contacts) who could help us locate the participant in the future. The staff will prompt participants to provide contact information for social service providers who may have regular and direct contact with participants. Investing time in gathering this contact information at the initial visit will pay off with higher retention at all study visits.

Staff will ask each participant for their preferred method of contact and use that preferred method first when attempting to contact them. If this method is unsuccessful, other available contact information will be used. If two consecutive attempts to reach the participant have been unsuccessful, progression to a secondary contact will be made. Staff will not attempt to contact any individual more than twice a day. Staff will refer to their local contact tracking log prior to
contacting the participant to ensure that other study staff have not already contacted them. All retention attempts, including follow-up calls, reminder calls, text messages, and emails should be entered into the local contact tracking log and should reference the outcome and any next steps to be taken. When participants are repeatedly nonresponsive via phone (or their preferred means of communication), staff should consider alternative methods including but not limited to their secondary contacts, social media, text messaging, email, and paper mail. Retention efforts following missed appointments should be conducted at least weekly per participant and up to twice a week as needed, depending on participant responsiveness. Old, inaccurate, or disconnected means of communication should be labeled as such. A participant should not be considered "lost to follow-up" until all avenues of outreach have been pursued to confirm the participant's status. Staff will consult with the SC Project Lead and Study Manager prior to determining if the participant is considered lost to follow-up. If a participant re-initiates contact, a new Contact Information Worksheet with current information should be completed prior to the next scheduled visit.

7. Study Visits and Procedures

The following study assessments and procedures will be performed on each participant, after signed informed consent is obtained, as part of participation in this study. See Appendix 2 for a tabulated summary of the measures and assessments described below and Appendix 1 for their schedule of completion.

7.1 Pre-Screening

Pre-screening will occur through the online pre-screener (see Section 5.2). Potential participants found eligible based on the online pre-screener will be contacted by a Research Coordinator, Outreach Coordinator, or designee at a participating SC to provide them information about the study. Participants who pre-screen as eligible and agree to learn more about the study will be scheduled for the Enrollment Visit at a participating SC or via video conferencing.

7.2 Enrollment

In-person participants may complete the Enrollment Visit in 1 day or 2 separate days, based on site discretion. Virtual participants will complete this visit in 2 or 3 separate days. In both cases, the entire enrollment visit must be completed within 28 days of pre-screener completion.

All participants will complete items in Section 7.2.1 on the first day of the enrollment visit.

If the in-person visit is split into 2 separate days, participants should complete the items in biospecimen collected noted in Section 7.2.3 and the Measures and Assessments related to the primary outcomes in Section 7.2.2 on Day 1, with the remaining items being completed on Day 2, as needed.

For the virtual participants, only the items listed in Section 7.2.1 can be completed on Day 1. On Day 2, participants should complete, at minimum, the items in biospecimen collected noted in Section 7.2.3 and the Measures and Assessments related to the primary outcomes in Section 7.2.2. Remaining items can be completed on Day 3, as needed.

Regardless of the number of days for the Enrollment Visit, the primary outcome measures and assessments listed in Appendix 2 should always be completed on the same day as biospecimen collection.

7.2.1 General

- Administer informed consent
- Confirm eligibility
- Enroll participant
- Complete Contact Information Worksheet
- Evaluate for social harms, adverse events (AEs)/serious adverse events (SAEs), and unanticipated problems (UPs)

7.2.2 Measures and Assessments

(See Appendix 2 for a detailed list.)

- Staff-administered
- Self-administered

Virtual Participation – For the Enrollment and Follow-up Visits, participants will complete the self-reported questionnaires and specimen collection forms via an online secure link (that is unique to that study participant) sent to participants via electronic Patient Reported Outcomes (ePRO), a web-based, HIPAA-compliant platform for collecting data via direct data entry. Once the participant completes the self-reported questionnaires and specimen collection forms, they are asked to log out and close their browser to ensure confidentiality of their responses. The research staff will then verify completion of the self-reported questionnaires and specimen collection forms.

The staff-administered questionnaires will take place via video conferencing. A secure hyperlink to access the video conference will be sent to the participant via a HIPAA-compliant secure messaging email or texting platform. Special arrangements may be made to complete the surveys and questionnaires over the phone with research staff, as applicable.

7.2.3 Biospecimen Collection

- In-Person Participants
 - POCT:
 - All participants
 - Toxicology screening, urine (iCup®)
 - For participants who report NLWHIV, are unsure of their HIV status, or decline to answer:
 - HIV antibody test, saliva
 - Local Laboratory Testing (venipuncture)
 - For participants who report NLWHIV, are unsure of their HIV status, or decline to answer:
 - Instrumented HIV Ag/Ab test
 - Plasma storage
 - For participants who report LWHIV:
 - HIV viral load testing
 - Plasma storage
 - Central Laboratory Testing (venipuncture)
 - For participants who report NLWHIV, are unsure of their HIV status, or decline to answer)
 - PrEP adherence monitoring, dried blood spot (DBS); prepared within the clinic or by the local laboratory staff
- Virtual Participants
 - At-Home POCT (self-testing):
 - All participants
 - Toxicology screening, urine (iCup®)
 - For participants who report NLWHIV, are unsure of their HIV status, or decline to answer:
 - HIV antibody test, saliva
 - Central Laboratory Testing (fingerstick, self-collected by participant)
 - For participants who report NLWHIV, are unsure of their HIV status, or decline to answer:

- DBS PrEP adherence monitoring
- For participants who report LWHIV:
 - HemaSpot blood collection device (or equivalent) HIV viral load testing

Virtual Participation – After Day 1 of the Enrollment Visit, where the participant will consent to the protocol and contact information will be collected, self-administered lab evaluation kits will be mailed to participants. The toxicology screening and HIV antibody test will be done in real time and the participants will present their results to the study team via video conferencing and/or photo upload of results. The study team will then document results in the EDC system. The DBS and HemaSpot will be mailed to a central lab for analysis.

Section 11.1 contains additional information relating to biological specimens.

7.3 On-Study

The following assessments will be performed at Month 4, Month 8, and Month 12. Visit windows are defined in Section 3.2.5 and included in the Schedule of Events in Appendix 1.

If the follow-up visit is split into 2 days, the primary outcome measures and assessments listed in Appendix 2 should **always** be completed on the same day as biospecimen collection. The entire follow-up visit must be completed within 28 days of the initial follow-up encounter.

Please note, if randomized to the intervention arm, a participant is not required to finish all intervention sessions to complete follow-up visits; it is acceptable to miss sessions and continue in follow-up. However, once the Month 4 visit is conducted, no further intervention sessions can occur.

7.3.1 General

- Review/update Contact Information Worksheet
- Evaluate for social harms, AEs/SAEs, and UPs

7.3.2 Measures and Assessments

(See Appendix 2 for a detailed list.)

- Staff-Administered
- Self-Administered
- Brief qualitative exit interview (at Month 4 or Premature Discontinuation, for selected intervention participants only)

7.3.3 Biospecimen collection

See Section 7.2.3 as the On-Study biospecimen collection is identical to the enrollment biospecimen collection.

7.4 **Premature Discontinuation**

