2.2 Study Endpoints

2.2.1 Primary Endpoint

• Distinct acts of CAS defined as anal sex acts without the use of a condom or without the protection of prevention-effective PrEP (for participants NLWHIV) or viral suppression (for participants LWHIV) over the course of study follow-up

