7.5 Efficacy Assessments

All study assessments are listed in Appendix 2. In brief, primary efficacy will be determined by a combination of self-report and biomarkers at each follow-up visit. Participants will be asked to report the number of times (continuous) in the past 4 months they have engaged in CAS with a male partner. Those who report oral PrEP use will also provide blood samples for assessing PrEP adherence, and those who report injectable PrEP use will be asked to provide a medical record release to confirm receipt of their bimonthly injections. Similarly, those who are LWHIV will provide blood samples for viral load testing.

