8.1 HIV Testing

The local laboratory will perform testing for HIV diagnosis at enrollment and other scheduled visits for in-person participants. SCs will follow local algorithms for HIV testing, and those algorithms should be shared with the Central Laboratory prior to site activation. For virtual participants, HIV testing will be performed using self-collected at-home rapid testing kits for participants NLWHIV and participants who are unsure of their status. Participants who test reactive on the rapid test will be referred to local HIV care services/resources in their respective areas. Linkage-to-care will involve one-on-one follow-up phone calls by trained study staff who will provide referral information for ongoing HIV treatment in their respective area.

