8.2 HIV Viral Load Testing

For participants LWHIV, viral suppression will be assessed for in-clinic and virtual participants. For in-person participants, viral load testing should be done using an FDA-cleared assay with a limit of detection of 40 copies/mL or lower. For virtual participants, capillary (fingerstick) blood will be self-collected on a DBS card and sent for viral load testing at the Central Laboratory, or a laboratory designated by the Central Laboratory.

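### Blood markers are assigned by self-reported HIV status, so a participant whose study HIV test is reactive but who does not report living with HIV has no viral load for the primary endpoint

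*Protocol*

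**What the plan says.** The primary endpoint (Section 2.2.1) counts condomless anal sex acts that lack protection. Protection is judged by a status-specific marker: "prevention-effective PrEP (for participants NLWHIV) or viral suppression (for participants LWHIV) over the course of study follow-up". Section 14.3.3 repeats this in the estimand.

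Section 7.2.3 decides which samples are taken. One branch is headed "For participants who report NLWHIV, are unsure of their HIV status, or decline to answer". It receives HIV testing and a dried blood spot for PrEP adherence and, for in-person participants, plasma storage. The other branch is headed "For participants who report LWHIV" and receives viral load testing. For virtual participants neither branch lists plasma storage. Section 7.3.3 applies the same rule at every follow-up visit: "the On-Study biospecimen collection is identical to the enrollment biospecimen collection".

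Two other sections describe viral load by status, not by report. Section 7.5 says "those who are LWHIV will provide blood samples for viral load testing", and Section 8.2 says "For participants LWHIV, viral suppression will be assessed for in-clinic and virtual participants".

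On a reactive result, Section 8.1 says for the at-home rapid test: "Participants who test reactive on the rapid test will be referred to local HIV care services/resources in their respective areas". It adds follow-up calls for linkage to care. In-person sites follow local testing algorithms, whose content is not given.

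**The concern.** Two classifiers are in use: reported status for collecting specimens, and HIV status for defining the endpoint. They agree for most participants. They disagree when the study's own HIV test contradicts the participant's report, and then Section 7.2.3 calls for a PrEP sample while Sections 7.5 and 8.2 call for a viral load.

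Such disagreement is foreseeable. The trial tests for HIV at every visit, admits people unsure of their status and lets them decline to state it. Section 1.2 describes undiagnosed infection as more common in this population. A mismatch means either a new infection or one not disclosed, and both are central to an endpoint about transmission risk. An analysis plan can define how to score these acts, but it cannot supply a viral load that was never drawn. HIV status is also a planned subgroup factor in Section 14.3.3, with no statement of whether it means reported or tested status.

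**Working it through.** The protocol states no figure to reproduce here. The check sets the Section 7.2.3 collection rule against the marker that Section 2.2.1 needs.

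**Routing at any one visit**

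| Reported status | True status | Marker drawn (7.2.3) | Marker needed (2.2.1) | Result |
|---|---|---|---|---|
| Not living with HIV | negative | PrEP | PrEP | agrees |
| Not living with HIV | positive | PrEP | viral load | missing |
| Unsure | negative | PrEP | PrEP | agrees |
| Unsure | positive | PrEP | viral load | missing |
| Declines | negative | PrEP | PrEP | agrees |
| Declines | positive | PrEP | viral load | missing |
| Living with HIV | negative | viral load | PrEP | missing |
| Living with HIV | positive | viral load | viral load | agrees |

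Four of eight cells agree. The three cells missing a viral load are the subject here. The remaining mismatch (reports living with HIV, truly negative) is a corner case: that branch has no HIV test, so the study's own result could not reveal it. Nothing below rests on it.

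**Duration.** The rule is reapplied at Months 4, 8 and 12. At the visit of first reactivity the viral load is missing under Section 7.2.3. At later visits it stays missing only while the participant does not report living with HIV.

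**Is there another route to the marker?**
- In-person: plasma is stored in the non-LWHIV branch, so a later viral load may be possible, but the protocol does not provide for one.
- Virtual: no plasma is listed. Section 8.2 describes virtual viral load from capillary blood on a dried blood spot card, and Section 11.1.3 keeps leftover specimens for at least 12 months after the last participant's last visit. Section 7.2.3, however, names a separate collection device for viral load, and nothing says that the leftover PrEP spot would suffice.
- Questionnaires: the Appendix 2 footnotes also route the PrEP and HIV-care forms by reported status, so they have the same gap.
- Estimand: seroconversion is not among the intercurrent events in Section 14.3.3.

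**Size, on an assumed proportion.** The protocol gives no share of participants who test reactive without reporting infection. Assume 0.5% to 5% of those randomized (Section 14.2: 360, as 240 IMPACT and 120 eSOC):
- Overall: 360 × 0.005 = 1.8, to 360 × 0.05 = 18
- IMPACT: 240 × 0.005 = 1.2, to 240 × 0.05 = 12
- eSOC: 120 × 0.005 = 0.6, to 120 × 0.05 = 6
- Virtual (about 180, Section 3): 180 × 0.005 = 0.9, to 180 × 0.05 = 9

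Ignoring attrition, there are 360 × 3 = 1,080 follow-up visits. If each affected participant lacks the marker at one follow-up visit, that is 1.8/1,080 = 0.2% to 18/1,080 = 1.7% of them. If each lacks it at all three, it is 5.4/1,080 = 0.5% to 54/1,080 = 5%.

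**The case against.** The strongest reply is that this is a wording mismatch with little effect. The endpoint is defined by HIV status, Section 7.5 already asks for viral load from those who have HIV, and scoring detail belongs in the analysis plan. The gap also tends to close: a participant who learns of the diagnosis through linkage calls and then reports it gets a viral load from the next visit. The count would differ only in some cases. If no effective PrEP level is found, the acts count as unprotected, just as they would for an unsuppressed new infection. No imbalance between arms has been shown.

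Most of this stands and limits the point. It does not remove it: Section 7.2.3 is the operative collection list, it omits the viral load at the first-reactive visit, and nothing in the protocol resolves its conflict with Sections 7.5 and 8.2.

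A reader might infer more, and the documents do not support it:
- **That these acts are scored on the PrEP level.** No section says so. The needed marker is missing and the scoring is unstated.
- **That everyone who declines to give their status is affected.** They are HIV-tested, and for those who are negative the PrEP sample is the right one.
- **That referral is the only consequence of any reactive result.** That sentence concerns the at-home rapid test; in-person sites follow local algorithms.
- **That the loss is irreparable for virtual participants.** The use of leftover dried blood is neither provided for nor ruled out.

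**Conclusion.** The point holds in a limited form. Sections 7.2.3 and 7.3.3 collect by reported status, while the primary endpoint and Sections 7.5 and 8.2 depend on HIV status. A participant who is HIV positive by the study's test but has not reported it has no viral load at that visit, and none later until they report it. The gap is firmest for virtual participants, for whom no stored plasma is listed.

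The number affected is probably small: about 2 to 18 of 360 under an assumed 0.5% to 5%, a range that does not come from the protocol. No effect on the rate ratio has been shown, and none is claimed. The change is still worth making because the specimen rule must be right at the time of collection.

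**What to change.** - **Collection.** Reconcile Sections 7.2.3 and 7.3.3 with 7.5 and 8.2. The viral load branch should apply to anyone who reports living with HIV or has a reactive study HIV result at that or an earlier visit, confirmed where the testing algorithm provides for it.
- **First-reactive visit.** For in-person participants, run the endpoint viral load on the plasma already stored.
- **Later virtual visits.** Put the viral load collection device already used in the study in the kits of participants with an earlier reactive result.
- **Classification.** Use the same tested-status rule for the endpoint and for the HIV-status subgroup factor.
- **Scoring the first-reactive interval.** Prespecify this, for example as missing viral load with a sensitivity analysis. Do not automatically count every act in the interval as unsuppressed. Recall covers four months, so some acts may precede acquisition and have been PrEP-protected, and a participant with an undisclosed infection may have been suppressed throughout.

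The cost is wording changes in the protocol, laboratory chart and analysis plan, and a few extra viral load assays.

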7.4.1 Assessments for Participants Discontinuing from Study Intervention

• Document reason for study intervention discontinuation.

- Those who request to stop participating in the study intervention will be asked for the reason(s) for stopping, and a subset will be asked to complete an exit interview.
- In addition, the participant will continue to complete all study follow-up visits, unless the participant decides to discontinue participation in the study entirely.

7.4.2 Assessments for Participants Discontinuing from the Study

- Document reason for discontinuing from the study.
- Those who request to stop participating in the study will be asked for the reason(s) for stopping and if they are willing to complete one final study visit.

7.5 Efficacy Assessments

All study assessments are listed in Appendix 2. In brief, primary efficacy will be determined by a combination of self-report and biomarkers at each follow-up visit. Participants will be asked to report the number of times (continuous) in the past 4 months they have engaged in CAS with a male partner. Those who report oral PrEP use will also provide blood samples for assessing PrEP adherence, and those who report injectable PrEP use will be asked to provide a medical record release to confirm receipt of their bimonthly injections. Similarly, those who are LWHIV will provide blood samples for viral load testing.

7.6 Safety Assessments

Reportable AEs/SAEs will be solicited from participants at enrollment and Months 4, 8, and 12. All events will be recorded using the designated form and will be reported in the data entry system.

See Section 13.3 for definitions of reportable safety events. Details regarding specific forms can be found in the Advantage eClinical[®] eCRF Completion Guide.

8. Description of Study Assessments and Measures

8.1 HIV Testing

The local laboratory will perform testing for HIV diagnosis at enrollment and other scheduled visits for in-person participants. SCs will follow local algorithms for HIV testing, and those algorithms should be shared with the Central Laboratory prior to site activation. For virtual participants, HIV testing will be performed using self-collected at-home rapid testing kits for participants NLWHIV and participants who are unsure of their status. Participants who test reactive on the rapid test will be referred to local HIV care services/resources in their respective areas. Linkage-to-care will involve one-on-one follow-up phone calls by trained study staff who will provide referral information for ongoing HIV treatment in their respective area.

